Participants will be given contact information to a dedicated staff if they have any questions of concerns regarding the study and their participation in the study. Additional psychological risk may occur as the study involves bringing up sensitive topics such as risky sexual behavior and personal data, to minimize this risk, participants will be ensured that their information is protected with the utmost care and that all their gathered information will only be used for researched purposes. Any adverse events will be recorded.

Statistics

Sample size calculation

The sample size was be calculated with the following components:

- α (two-tailed) of 0.05
- $\bullet \qquad \beta = 0.8$
- Obtained from a study with a peer-led safe sex online intervention for Hong Kong adolescents aged <25 (19)
 - o Standard deviation: 0.52
 - o Effect size: 0.21

Attrition rate: 15% in online studies (20, 21)

112 people per intervention arm

Data Analysis

Data will be analyzed using SPSS. Descriptive statistics will be carried out analyze the demographics of the target population. Differences in baseline demographic characteristics between the intervention and control group will be assessed using chi-squared tests.

For outcome evaluation, paired t-tests will be used to examine within group outcome changes. For the primary outcome that is a score, linear regression will be used to evaluate the difference between the control and intervention group.

Independent t-tests will be carried out to evaluate the score change within group and also between groups. The outcome difference at baseline and at follow-up will also be evaluated with linear regression.

Direct Access to Source Data/Documents

The investigator/institution will permit trial-related monitoring, audits, IRB/IEC review, regulatory inspections, providing direct access to source data/documents.

Quality Control and Quality Assurance

Ethics

Major ethical issues involve asking about sensitive information regarding risky sex behaviors, users' privacy, and legal issues. Participants will be ensured by the project's researchers that their information is kept strictly confidential. Researchers will also ensure that participants understand the purpose and procedure of every step of the project and participants will be provided with a contact for whenever they have any questions or concerns. Patients also understand that they are allowed to withdraw at any given point of the study.

Data Handling and Record Keeping

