Evaluation of a	ı peer-led we	b-based int	tervention f	or safe usa	ige of d	ating
applica	tions in Hong	g Kong: a r	andomized	controlled	trial	

Statistical Analysis Plan

August 2018

(Version 1. Dated 17.08.2018)

Principle Investigator: [name]
Address: Department of Family Medicine and Primary Care, [name]
Co-Investigators: [name], [name]

Statistical Methods

The demographics were described and differences in baseline were assessed using chi-square tests for categorical variables for e.g. age, gender and sexual orientation; and, *t*-test for scaled outcomes. The satisfaction of the intervention at post-intervention was analysed using chi-square test. ITT with the "last observation carried forward" values was adopted. Due to the skewness distribution of the outcomes, the differences of intervention at follow-ups were assessed using Mann-Whitney U-test. Univariate linear regression and multiple linear model was used to evaluate the significant factors between the intervention and control groups and after the adjustment of baseline outcome measurements respectively. All data were entered, cleaned and analysed using SPSS (Version 25) and significant tests were set at P-values <0.05.

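### No deciding test is fixed: the Protocol gives the primary score linear regression without saying whether it uses baseline, and the SAP lists Mann-Whitney, unadjusted and baseline-adjusted regression without naming one as primary

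*SAP*

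**What the plan says.** **Protocol.** Delivery of Intervention places the primary endpoint 1 month after delivery and also schedules a baseline and an immediate post-intervention questionnaire. Statistics, Data Analysis then says: "For the primary outcome that is a score, linear regression will be used to evaluate the difference between the control and intervention group". The score is not named, and neither is any covariate. Two further between-group analyses follow: "Independent t-tests will be carried out to evaluate the score change within group and also between groups" and "The outcome difference at baseline and at follow-up will also be evaluated with linear regression". The last could mean a regression of change, separate models at each time point, or adjustment for baseline.

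**SAP, Statistical Methods.** No outcome, time point or test is called primary. The comparison of arms is given as: "Due to the skewness distribution of the outcomes, the differences of intervention at follow-ups were assessed using Mann-Whitney U-test". The next sentence reads "Univariate linear regression and multiple linear model was used to evaluate the significant factors between the intervention and control groups", and continues "after the adjustment of baseline outcome measurements respectively", which attaches baseline adjustment to the multiple model only. One threshold covers everything: "significant tests were set at P-values <0.05".

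**The concern.** A reader of both documents cannot tell which P-value decides the trial. Two choices are open.

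- **Regression or Mann-Whitney.** The Protocol designates regression. The SAP introduces a rank test because of skewness and neither repeats nor withdraws the designation. The two tests also address different quantities: a difference in means, on which the sample size rests, and a comparison of ranks.
- **With or without the baseline score.** The Protocol's primary sentence is silent. The SAP runs both versions and does not choose.

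If these are settled after the results are known, the conclusion can depend on the choice. There is also an efficiency loss: the baseline score is already collected, and leaving it out of the deciding analysis gives up power.

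**Working it through.** **Reproduce the plan's figure.** From the Protocol, Sample size calculation: two-sided alpha 0.05, power 0.80 (printed as beta), SD 0.52, effect 0.21, attrition 15%.

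- n per arm = 2 × (0.52 × (1.960 + 0.842) / 0.21)² = 96.3, so 97.
- 97 × 1.15 = 111.6, so 112, the stated figure. It reproduces with 0.21 as a mean difference in an unadjusted comparison of two means.
- Analysed after 15% loss: 112 × 0.85 = 95.2, so 95 per arm.
- Standardised difference: 0.21 / 0.52 = 0.404.

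**Assumptions not in the documents.** Baseline/follow-up correlation r of 0.3, 0.5 or 0.7; equal arms; individual randomisation; the shape of the score.

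**Power at 95 per arm, normal scores, by formula.**

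- Unadjusted regression: non-centrality 0.404 × √(95/2) = 2.78; power 79%.
- Mann-Whitney: efficiency 3/π = 0.955 relative to the t-test, so 2.78 × √0.955 = 2.72; power Φ(2.72 − 1.96) = 78%. Simulation gives 77%.
- Adjusted regression: residual SD 0.52 × √(1 − r²) = 0.496, 0.450, 0.371; power 83%, 89%, 97%. Repeated simulations span 82–98%.

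**How often verdicts at 0.05 differ under the planned effect, by simulation.** Ranges run over r = 0.3 to 0.7. The skewed case uses exponential scores (skewness 2). The effect is either a pure shift, or a multiplication of the intervention arm's scores by about 1.52, which gives the same standardised difference: (1.52 − 1) / √((1 + 1.52²)/2) = 0.404.

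| Scores and effect | Mann-Whitney power | Unadjusted power | Adjusted power | Mann-Whitney v. adjusted differ |
|---|---|---|---|---|
| Normal, shift | 77% | 79% | 82–98% | 9–22% |
| Skewness 2, shift | 98% | 79–80% | 83–97% | 4–17% |
| Skewness 2, multiplicative | 70% | 80–81% | 83–98% | 19–28% |

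The two regressions differ in about 7–19% of trials in each row. Skewness alone therefore does not say which test is stronger; that depends on the form of the effect.

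**Under no effect.** Each test alone rejects in about 5% of trials. If significance on either regression counted as success, the rate would be 6–8%; on any of the SAP's three tests, 7–10%.

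**Carry-forward.** The SAP applies "last observation carried forward", which would return dropouts to the analysis. In the worst case (112 per arm, all 15% carrying the baseline score, normal scores) power is 70–71% for Mann-Whitney, 72% unadjusted and 79–97% adjusted. The order does not change. The dilution may be smaller where the immediate post-intervention value is carried.

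**Clustering.** Protocol, Study design, allows Yijin students to be randomised by cluster. Take, as an assumption, 8 classes of 25, all clustered. The design effect 1 + 24 × ICC is 1.48 at ICC 0.02 and 2.2 at 0.05. A model that ignores it has type I error 2 × (1 − Φ(1.96/√1.48)) = 11% and 2 × (1 − Φ(1.96/√2.2)) = 19%. If instead the baseline score at r = 0.5 removes only within-class variation, the residual variance is 1 − 0.25 = 0.75 and the ICC rises to ICC/0.75. The design effects become 1.64 and 2.6, and the errors about 13% and 22%.

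**The case against.** **The Protocol governs and its primary regression is plainly unadjusted.** The primary sentence names no covariate, baseline is handled in a separate sentence, and 112 reproduces from an unadjusted formula. This is a fair reading of the Protocol. But the SAP does not confirm it, and an unadjusted sample size formula does not fix the analysis model. Preferring the adjusted model is partly a case for efficiency, and should be read as such.

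**Skewness justifies Mann-Whitney.** It can be a legitimate choice, and pre-specifying it would also end the ambiguity. It would, however, change the Protocol's stated method, leave out the baseline score, and lose power if the effect is multiplicative.

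**Stronger readings that the documents do not support.**

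- A reader might infer that the SAP replaces regression with Mann-Whitney and so contradicts the Protocol outright. The SAP keeps regression in two forms. Its wording about significant factors is clumsy and could be taken as a search for predictors, but the reference to the two groups and to baseline adjustment points to treatment comparisons.
- A reader might infer that type I error is inflated to 6–10%. That needs a rule that any significant test counts as success, and neither document states one.
- A reader might infer from the SAP's past tense that the test was chosen after seeing the data. The documents do not show this.

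Differing verdicts under a real effect largely reflect differing power. They are not evidence of bias in any one test.

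**Conclusion.** The point holds in this form: the Protocol designates regression for the primary score, the SAP sets Mann-Whitney and two regressions side by side without ranking them, and neither document says that the deciding regression uses the baseline score. Under the normal-score assumptions above, the choice moves power between about 77% and 98% and changes the verdict in up to about a fifth of trials. The figures depend on the assumed correlation and, under skew, on the form of the effect; they are not bounds. They also assume individual randomisation, which the Protocol leaves open. This should be corrected. It does not invalidate the trial, because under individual randomisation each test is valid on its own.

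**What to change.** In both documents:

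- Name the primary score. Make linear regression of its 1-month value on arm and baseline score the single primary analysis, fixed whatever distribution is seen. Apply P<0.05 for the trial's conclusion to that test only.
- Deal with skewness through a robust or bootstrap 95% confidence interval for the same coefficient.
- If any Yijin students are randomised by class, make the same model account for the class, by a mixed model or by cluster-robust errors with a small-sample correction. Without this, a single fixed primary model could build in a larger error than the ambiguity it removes.
- Label Mann-Whitney, the unadjusted regression and the change-score analyses as supportive, and the immediate post-intervention and other scores as secondary.
- Reword the SAP's regression sentence to say that its models estimate the treatment effect.

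**Cost.** Wording only. The baseline score is already collected and the SAP already lists the adjusted model; class membership must be recorded if classes are randomised. The downside is a possible loss of power against Mann-Whitney if the score is strongly skewed and the effect is close to a pure shift (83–97% against 98% at skewness 2). In return, the estimate stays on the mean-difference scale used for the sample size.

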The primary endpoint will be 1 month after the delivery of the intervention. Students will fill out a baseline questionnaire before the delivery of the intervention and an immediate post questionnaire. 1 month later, students will access a follow-up questionnaire via HKU Survey Gizmo, a secure survey tool to ensure all data is kept confidential. The details of the delivery method of the follow-questionnaire will be discussed with the college's staff. Research staff may attend a special session or class to delivery the follow-up questionnaire. Another option is to have teachers deliver the follow up questionnaire. The follow-up questionnaire will be online hence participants will be able to access it on their computers, phones, or other mobile devices. Participants are estimated to participant in the trial for no longer than 4 months. Participants are allowed to withdraw from the study at any point in time without any criterion.

Selection and Withdrawal of Subjects

Inclusion criteria

- Aged 17-27
- Able to read and understand Chinese
- Able to provide an active email

Exclusion criteria

- People who have a physical impediment in which they cannot access the material in the intervention

Participants are allowed to withdraw from the study at any point in time without any criterion. We will utilize the "intention to treat" approach to deal with subjects withdrawn.

Treatment of Subjects

The intervention is a web based intervention and will not involve any medical treatments, drugs, or pharmaceuticals. The route of administration is access through any device that can access web-based content and the dosage is one visit.

Assessment of Efficacy

Evaluation will be done with an online survey tool called HKU Survey Gizmo. There will be a pre questionnaire containing baseline demographics and other questions concerning dating application usage. The participants will be given 30-45 minutes to access the program. Following that, the participants will be given a post questionnaire. 1 month later, the participants will be asked to fill in a follow up questionnaire.

Assessment of Safety

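### The primary score is never named and the SAP drops the protocol's 1-month time point, so the 5% alpha behind the sample size belongs to no identifiable test

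*SAP*

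**What the plan says.** **Protocol.** Trial Objectives and Purpose lists four effectiveness aims (information, awareness, attitudes, behavioural skills) without ranking them. Delivery of Intervention schedules a questionnaire at baseline, one straight after the session and one at 1 month, and states "The primary endpoint will be 1 month after the delivery of the intervention". That fixes a time, not a measure. Assessment of Efficacy names the survey tool but no scale. Data Analysis begins the rule for the between-arm comparison with "For the primary outcome that is a score" and assigns linear regression to it. It also lists t-tests of score changes. The sample size section uses "α (two-tailed) of 0.05", "Standard deviation: 0.52", "Effect size: 0.21" and "Attrition rate: 15% in online studies" to reach 112 per arm. The SD and effect come from an earlier safer-sex trial and are tied to no score in this one.

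**SAP, Statistical Methods.** No primary outcome and no primary time point are given. The outcomes are described as skewed, and "the differences of intervention at follow-ups were assessed using Mann-Whitney U-test". Unadjusted and baseline-adjusted linear regressions follow. One threshold covers everything: "significant tests were set at P-values <0.05". Neither document has a multiplicity adjustment, a ranking of outcomes or a rule for declaring the intervention effective.

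**The concern.** An alpha of 5% protects a conclusion only if the test that carries it is fixed in advance. Here the sample size rests on one two-sided 5% test, but three things needed to identify that test are open:

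- **Score:** neither document names it.
- **Time point:** the protocol chose 1 month, and the SAP does not carry that choice over.
- **Method:** the protocol gives linear regression for the primary outcome, while the SAP gives a Mann-Whitney test and two regressions.

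Someone following the SAP to the letter could report whichever score and method reached significance and present it as the main result. Both the claim of effectiveness and the meaning of the 112 per arm would be affected.

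**Working it through.** **1. The plan's own figure.** Inputs from the protocol's sample size section: two-sided alpha 0.05, SD 0.52, difference 0.21, attrition 15%. The printed β of 0.8 only makes sense as power. Two equal arms are assumed, since a single per-arm figure is given.

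n = 2 × [0.52 × (1.960 + 0.842) / 0.21]² = 96.25, rounded up to 97 per arm.

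97 × 1.15 = 111.6, rounded up to 112, which matches the protocol. Dividing by 0.85 would give 115; the difference is minor, since power with 112 × 0.85 ≈ 95 evaluable per arm is 79.6%. Read as a standardised effect, 0.21 would need 356 per arm before attrition, so it must be a raw difference. The 112 therefore presumes one test, of one score, at 0.05.

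**2. Error rate if several scores carry the claim.** The documents do not give the number of scores. Assume k scores, each tested at 0.05, with any one significant result claimed as effectiveness. For independent tests:

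- either direction: 1 − 0.95^k
- favouring the intervention only: 1 − 0.975^k

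Correlated cases come from 500,000 simulated draws of normal test statistics, with assumed correlations of 0.3 to 0.7 between scores and, where both times count, 0.6 between times.

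| Tests | Either direction, independent | Either direction, correlated | Favouring intervention, independent | Favouring intervention, correlated |
|---|---|---|---|---|
| 2 scores, 1 month | 9.8% | 9.5% to 8.3% | 4.9% | 4.8% to 4.2% |
| 4 scores, 1 month | 18.5% | 17.3% to 13.1% | 9.6% | 8.7% to 6.6% |
| 5 scores, 1 month | 22.6% | 20.7% to 14.9% | 11.9% | 10.5% to 7.4% |
| 4 scores, both times (8 tests) | 33.7% | 28.8% to 21.9% | 18.3% | 14.6% to 11.0% |

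The nominal values for comparison are 5% in either direction and 2.5% in the favourable direction.

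**3. Choice of method alone.** Take one score at one time with 95 per arm, normal data and an assumed baseline correlation of 0.5. In 4,000 simulated trials with no effect, the Mann-Whitney test, unadjusted regression and baseline-adjusted regression were significant in 4.9%, 4.8% and 5.3%. At least one of the three was significant in 8.3%. Naming the score without naming the test therefore does not secure 5%.

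**4. What co-primary scores would cost.** Four scores with Bonferroni (0.05/4 = 0.0125 each) need 137 evaluable per arm, and 137/0.85 gives 162 enrolled. With 112 enrolled, power per score falls from 79.6% to 61.4%. Eight tests at 0.00625 need 157 evaluable and 185 enrolled, and power at 112 falls to 52.1%.

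**The case against.** A reader might infer that the plan runs eight equal tests, that any one of them proves effectiveness, and that the false-claim rate is therefore about one in three. The documents do not support that reading, for four reasons.

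- The protocol speaks of a primary outcome in the singular and puts the primary endpoint at 1 month. A hierarchy was intended; what is missing is the name of the score, and the SAP's failure to carry the time point over.
- The four objectives are aims, not scales. One score could cover several aims, or one aim could have several scores. The protocol also calls only the 1-month questionnaire a follow-up, so the SAP's plural makes two time points plausible but does not settle it.
- Neither document says that one significant result is enough. The SAP sets a threshold per test and is silent on the decision rule. That silence is a gap, not a rule.
- A false claim of effectiveness needs a result in favour of the intervention, which about halves the percentages.

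All four limit the size of the problem. None supplies the missing name, and an intended but unidentified primary outcome does not constrain the analysis.

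A reader might also infer from the SAP's past tense and its remark on skewness that outcome data had already been examined. The documents do not say so. The possibility matters only for how the choice must be labelled.

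**Conclusion.** The point holds in this form: the primary score is not identified, the SAP omits the protocol's 1-month primary time point, and the method for the primary comparison differs between the documents. That much is certain from the text.

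The size is conditional. For 2 to 5 independent scores at 1 month, with any one significant result claimed, the chance of at least one false positive is about 10% to 23% in either direction. For four scores it is 13% to 19% across the correlations considered, or about 7% to 10% counting only errors that favour the intervention. If four scores at the immediate questionnaire were given equal standing, the either-direction figure would be about 22% to 34%, but the protocol's choice of 1 month speaks against using that as the headline. No single percentage can be read from the documents, because the number of scores and the rule for claiming success are not stated.

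**What to change.** In both the protocol and the SAP:

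1. Name one questionnaire score of this trial, with its scale, at 1 month as the primary outcome. Confirm that a difference of 0.21 and an SD of 0.52 are plausible on that scale, since both come from another trial.
2. Specify one primary test at two-sided 0.05, reconciling the protocol's linear regression with the SAP's Mann-Whitney test. Baseline-adjusted linear regression is already in the SAP and would serve. The other analyses become sensitivity analyses.
3. Label all other scores, and the results of the immediate questionnaire, as secondary or supportive. Report them with estimates and confidence intervals, or with Holm adjustment if significance is to be claimed.
4. Fix the choice before outcome data are examined. If they have already been examined, label the analysis post hoc, because naming a primary outcome afterwards does not restore the 5%.

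The cost is a few lines in each document. The 112 per arm stands if the check in step 1 is satisfied. The downside is small: secondary scores can no longer support the main claim at an unadjusted 0.05.
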